7.7 EXTENT OF EXPOSURE

Only descriptive statistics are planned for this section of the CTR.

7.8 SAFETY ANALYSIS

All safety analyses will be performed on the TS.

7.8.1 Adverse events

AEs will be coded with the most recent version of MedDRA.

The analyses of AEs will be descriptive in nature. All analyses of AEs will be based on the number of subjects with AEs and not on the number of AEs.

For analysis, multiple AE occurrence data on the eCRF will be collapsed into one event provided that all of the following applies:

- All AE attributes are identical (lower level term, intensity, action taken, therapy required, seriousness, reason for seriousness, relationship, outcome, AESI)

- The occurrences were time-overlapping or time-adjacent (time-adjacency of two occurrences is given if the second occurrence started at most 1 hour after the first occurrence ended)

For further details on summarization of AE data, please refer to "Handling and summarization of adverse event data for clinical trial reports and integrated summaries" ([6](#)) [001-MCG-156] and "Handling of missing and incomplete AE dates" ([3](#)) [001-MCG-156_RD-01].

The analysis of AEs will be based on the concept of treatment emergent AEs. That means that all AEs will be assigned to the screening phase or on-treatment phase as defined in [Section 6.1](#).

An overall summary of AEs will be presented. This overall summary will comprise summary statistics for the class of other significant AEs according to ICH E3 and for the class of AESIs.

CTP: *The following are considered as AESIs in this trial:*

- *Hepatic injury, as defined by the following alterations of hepatic laboratory parameters:*
 - *an elevation of AST and/or ALT ≥ 3 -fold ULN combined with an elevation of total bilirubin ≥ 2 -fold ULN measured in the same blood sample, and/or*
 - *marked peak aminotransferase (ALT, and/or AST) elevations ≥ 10 fold ULN.*

The investigator had to classify on the eCRF whether an observed AE was an AESI or not.

According to ICH E3 ([8](#)), AEs classified as "other significant" need to be reported and will include those non-serious and non-significant AEs

- (i) which are marked haematological or other lab abnormalities, or
- (ii) which were reported with "action taken = discontinuation" or "action taken = reduced", or
- (iii) which lead to significant concomitant therapy as identified by the Clinical Monitor/Investigator at a Medical Quality Review Meeting.

The frequency of subjects with AEs will be summarised by treatment, primary SOC and preferred term. AEs which were considered by the investigator to be drug related (primary endpoint) will be summarised separately. Separate tables will also be provided for subjects with SAEs, subjects with AESIs and subjects with other significant AEs (according to ICH E3 ([8](#))). The frequency of subjects with AEs and the frequency of subjects with AEs considered by the investigator to be drug related will also be summarised by maximum intensity, primary SOC and preferred term.

The SOCs will be sorted according to the standard sort order specified by the EMA, preferred terms will be sorted by total frequency (within SOC).

For disclosure of AE data on ClinicalTrials.gov, the frequency of subjects with non-serious AEs occurring with an incidence of greater than 5 % (in preferred terms) will be summarised by treatment, primary SOC and preferred term. The frequency of subjects with SAEs will also be summarised.

For disclosure of AE data in the EudraCT register, the frequency of AEs, the frequency of non-serious AEs with an incidence of greater than 5 % (in preferred terms) and the frequency of SAEs will be summarised.

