### Adverse events of special interest (AESIs)

The term AESI relates to any specific AE that has been identified at the project level as being of particular concern for prospective safety monitoring and safety assessment within this trial, e.g. the potential for AEs based on knowledge from other compounds in the same class. AESI need to be reported to the sponsor's Pharmacovigilance Department within the same timeframe that applies to SAE, please see above.

The following are considered as AESIs in this trial:

- Hepatic injury, as defined by the following alterations of hepatic laboratory parameters:
  - an elevation of AST and/or ALT  $\geq 3$ -fold ULN combined with an elevation of total bilirubin  $\geq 2$ -fold ULN measured in the same blood sample, and/or
  - marked peak aminotransferase (ALT, and/or AST) elevations  $\geq 10$  fold ULN

These lab findings constitute a hepatic injury alert and the patients showing these lab abnormalities need to be followed up according to the 'DILI checklist' provided in the ISF. In case of clinical symptoms of hepatic injury (icterus, unexplained encephalopathy, unexplained coagulopathy, right upper quadrant abdominal pain, etc.) without lab results (ALT, AST, total bilirubin) available, the Investigator should make sure these parameters are analysed, if necessary in an unscheduled blood test. Should the results meet the criteria of hepatic injury alert, the procedures described in the DILI checklist should be followed.

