#### Information required

For each AE, the investigator should provide the information requested on the appropriate CRF pages and the BI SAE form (if applicable). The investigator should determine the causal relationship to the trial medication. The following should also be recorded as an (S)AE in the CRF and on the SAE form (if applicable):

- Worsening of the underlying disease or of other pre-existing conditions

Proprietary confidential information © 2017 Boehringer Ingelheim International GmbH or one or more of its affiliated companies

- Changes in vital signs, ECG, physical examination and laboratory test results, if they are judged clinically relevant by the investigator.

If such abnormalities already pre-exist prior trial inclusion they will be considered as baseline conditions.

All (S)AEs, including those persisting after individual subject's end of trial must be followed up until they have resolved, have been sufficiently characterised, or no further information can be obtained.

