7.8.2 Laboratory data

The analyses of laboratory data will be descriptive in nature and will be based on BI standards (7). If possible, analyses will be based on original values. If multiple reference ranges apply for a parameter (e.g. due to different age groups), analyses will be based on normalised values, which means transforming to a standard unit and a standard reference range.

Descriptive statistics of laboratory values over time and for the difference from baseline (see [Section 6.7](#)) will be provided. Frequency tables of changes between baseline and last value on treatment with respect to the reference range will be presented.

Possibly clinically significant abnormal laboratory values are only those identified either in the Investigator's comments or at the RPM/DBLM at the latest. It is the Investigator's responsibility to decide whether a lab value is clinically significant abnormal or not. Standard or project-specific rules for flagging clinically significant values in an automated manner will not be applied in this study.

Clinically relevant findings in laboratory data will be reported as baseline conditions (at screening) or as AEs (during the trial) if judged clinically relevant by the investigator, and will be analysed as such.

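### The only adverse event of special interest is defined by laboratory thresholds, but the SAP counts it from the investigator's eCRF classification and describes no derivation from, or check against, the laboratory data

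*SAP*

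**What the plan says.** Protocol 5.2.2.1 names one AESI, hepatic injury, "as defined by the following alterations of hepatic laboratory parameters". There are two criteria, and SAP 7.8.1 repeats both:

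- AST and/or ALT at least 3-fold ULN, "combined with an elevation of total bilirubin" of at least 2-fold ULN in the same blood sample.
- "marked peak aminotransferase (ALT, and/or AST) elevations" of at least 10-fold ULN.

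SAP 7.8.1 then gives the source of AESI status for analysis: "The investigator had to classify on the eCRF whether an observed AE was an AESI or not". It lists AESI among the attributes of an AE record. The status feeds the overall AE summary and a table of its own: "Separate tables will also be provided for subjects with SAEs, subjects with AESIs and subjects with other significant AEs".

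Two further statements govern how a laboratory value becomes an AE. Under Information required, protocol 5.2.2.2 has investigators record as AEs changes in "laboratory test results, if they are judged clinically relevant by the investigator". SAP 7.8.2 says that relevant laboratory findings are reported "as AEs (during the trial) if judged clinically relevant by the investigator, and will be analysed as such". The same SAP section adds: "Standard or project-specific rules for flagging clinically significant values in an automated manner will not be applied in this study".

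**The concern.** The definition contains no judgement: given three laboratory values from a sample, a program can say whether it is met. The planned count nevertheless passes through two human steps. The finding must first be recorded as an AE, and that AE must then be marked as an AESI. If either step fails, the subject drops out of the AESI table, and the SAP text describes nothing that would bring the subject back.

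What is at stake is how a reported zero can be read. In groups of six, the reader of the trial report will want to know whether no subject met the criteria or whether none was marked as meeting them. The planned table answers only the second question, although the data for the first are collected.

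**Working it through.** The point rests on no sample-size, power or alpha figure, and the plan states no figure to reproduce. The check is textual, followed by a short illustration of size.

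**Step 1. Compare the definition with the source of the count.** The definition uses multiples of ULN only (protocol 5.2.2.1, SAP 7.8.1). The count uses an eCRF attribute of an observed AE (SAP 7.8.1). No section of the protocol or SAP links the two by program.

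**Step 2. See whether another planned laboratory output gives the same count.**

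| Output | Where | What it shows | What it does not show |
|---|---|---|---|
| Reference-range flag | Protocol 7.3.3 | Any out-of-range value | 3-fold, 2-fold or 10-fold ULN; same-sample pairing |
| Shift table | SAP 7.8.2 | Baseline against last on-treatment value, by reference range | Peaks that have resolved; multiples of ULN |
| Descriptive statistics, including the maximum | SAP 7 and 7.8.2 | An extreme ALT or AST at a time point | Number of subjects; same-sample pairing |
| Individual listings | SAP 7 | Every value, so a check by hand is possible | No such check is specified |
| Significant values identified from investigator comments or at the report planning/database lock meeting | SAP 7.8.2 | Values judged significant | Not linked to AESI status |

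On the shift table: for a subject who completes the trial, the last scheduled safety laboratory sample is at the end-of-trial visit on Day 176 (Flow Chart). That is 176 − 22 = 154 days after the last multiple dose, or 176 − 1 = 175 days after the single dose. A transient rise soon after dosing would not appear in it.

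**Step 3. Compare with how the SAP treats ECG.** ECG abnormalities also become AEs only on the investigator's judgement of relevance (SAP 7.8.4). Even so, SAP 5.3.2 derives notable findings and categories from the measured values by numeric thresholds. SAP 7.8.4 flags and lists the notable findings and gives frequency tables for the categorical endpoints. The hepatic AESI has no equivalent.

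**Step 4. Illustrate the size, assuming exactly one missed subject.** Inputs: 6 active subjects per dose group (protocol 3.1) and four multiple-dose groups, so the pooled BI multiple-dose column in SAP 6.1 holds 4 × 6 = 24. Intervals are exact (Clopper-Pearson) 95%. For 0/n the upper limit is 1 − 0.025^(1/n); for 1/n the lower limit is 1 − 0.975^(1/n), and the upper limit is the 97.5% point of a Beta(2, n − 1) distribution.

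| Column | With the case counted | With the case missed |
|---|---|---|
| One dose group, n = 6 | 1/6 = 16.7% (0.4 to 64.1%) | 0/6 = 0% (0 to 45.9%) |
| Pooled BI multiple dose, n = 24 | 1/24 = 4.2% (0.1 to 21.1%) | 0/24 = 0% (0 to 14.2%) |

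The documents give no probability of a missed classification, so none is estimated.

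**The case against.** The strongest reply is that a case would have to slip past many safeguards. Values at the thresholds are themselves a hepatic injury alert with checklist follow-up (protocol 5.2.2.1). The combined criterion is among the reasons for removing a subject (3.3.4.1). Appendix 10.1 requires repeat tests and histories reported through the CRF. All AESIs must be documented, and reported within 24 hours (5.2.2.2). Clinical laboratory results are part of the minimum data set for the documented Safety Review before each escalation (3.1). It can also be argued that the relevance judgement governs ordinary laboratory changes, whereas AESIs are collected without that qualifier.

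Most of this stands, and it makes a miss improbable. Two things remain. These are duties during conduct, and none is described as setting or correcting the analysed count. And because the SAP has the investigator classify an observed AE, the finding must first be entered as an AE; the documents do not say that a threshold value bypasses the relevance judgement at that step.

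A reader might infer that all automated flagging is off, or that no planned output could reveal a qualifying value. The documents do not support either. Only automated flagging of clinically significant values is excluded; reference-range flags remain, a 10-fold value should show as a maximum, and every value is listed.

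The ADS Plan and the sponsor standards cited for AE and laboratory displays (001-MCG-156 and 001-MCG-157) were not supplied. Any of them could contain a hepatic check.

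**Conclusion.** The point holds as a cheap improvement. On the SAP text, the count of an objectively defined event depends on investigator classification, with no described derivation from, or reconciliation with, the laboratory data. An omission is possible, not expected: it needs an oversight or a judgement of non-relevance that survives the conduct safeguards.

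The effect falls on the AESI line of the overall AE summary and on the AESI table. A reader might go further and infer that the primary endpoint is compromised. That does not follow: subjects with drug-related AEs would be miscounted only if the finding also went unrecorded as a drug-related AE and the subject had no other such event. The safety analysis is descriptive throughout, so no test result is at issue, and 0/6 against 1/6 illustrates scale and is not evidence of likely bias.

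The conclusion assumes that the standards and ADS Plan not supplied add no hepatic derivation. If one does, a cross-reference in SAP 7.8.1 settles the matter.

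**What to change.** Add to SAP 7.8.1 or 7.8.2 a derived flag for each of the two protocol criteria:

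- Apply it to all on-treatment AST, ALT and total bilirubin samples in the treated set, not only the last value, using the ULN that applies to each sample.
- For the combined criterion, require the aminotransferase and bilirubin values to come from the same sample.
- Tabulate subjects meeting each criterion by treatment, beside the investigator-classified AESI table, which stays.
- List every disagreement between the derived flag and the eCRF classification, and resolve it before database lock.

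The cost is one derivation (a flag per criterion), one small table and query work where the two sources disagree. No extra samples are needed.

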7.8.2 Laboratory data

The analyses of laboratory data will be descriptive in nature and will be based on BI standards (7). If possible, analyses will be based on original values. If multiple reference ranges apply for a parameter (e.g. due to different age groups), analyses will be based on normalised values, which means transforming to a standard unit and a standard reference range.

Descriptive statistics of laboratory values over time and for the difference from baseline (see [Section 6.7](#)) will be provided. Frequency tables of changes between baseline and last value on treatment with respect to the reference range will be presented.

Possibly clinically significant abnormal laboratory values are only those identified either in the Investigator's comments or at the RPM/DBLM at the latest. It is the Investigator's responsibility to decide whether a lab value is clinically significant abnormal or not. Standard or project-specific rules for flagging clinically significant values in an automated manner will not be applied in this study.

Clinically relevant findings in laboratory data will be reported as baseline conditions (at screening) or as AEs (during the trial) if judged clinically relevant by the investigator, and will be analysed as such.

